4.7.2 Histology

When indicated, tissue samples will be obtained in those subjects requiring surgery, which may occur up to 4 weeks after the ferumoxytol administration. The MR localization and histology will be compared. Only tissue that is routinely obtained will be used for this study.

4.7.3 Study Duration

Study duration is 2 years. If there are no adverse events, the already enrolled subjects may repeat the study visit (days 1, 2, 3 and 4). This may be repeated at least 30 days apart, for up to a total of 4 study visits. Laboratory testing (creatinine/GFR) to check kidney function (prior to GBCA on study) and a pregnancy test in women of child bearing potential will be done at each subsequent visit.

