4.2 Exclusion criteria

4.2.1 Subjects with clinically significant signs of uncal herniation, such as acute pupillary enlargement, rapidly developing motor changes (over hours), or rapidly decreasing level of consciousness.

4.2.2 Subjects who have a contraindication for MRI: metal in their bodies (a cardiac pacemaker or other incompatible device).

- 4.2.3 Subjects with known allergic or hypersensitivity reactions to parenteral iron, parenteral dextran, parenteral iron-dextran, or parenteral iron-polysaccharide preparations (Investigator's Drug Brochure, Combidex 2002; Advanced Magnetics Inc; Investigator's Drug Brochure, Code 7228; 2003 Advanced Magnetics Inc).
- 4.2.4 Subjects with known hepatic insufficiency or cirrhosis
- 4.2.5 Subjects with known or suspected iron overload (genetic hemochromatosis or history of multiple transfusions)
- 4.2.6 Subjects with symptoms or signs of hemodynamic instability.
- 4.2.7 HIV-positive patients on combination antiretroviral therapy are ineligible because of the potential for pharmacokinetic interactions with ferumoxytol.
- 4.2.8 Pregnant or lactating women are excluded from this study because of possible risk to the fetus or infant.
- 4.2.9 Subjects with three or more drug allergies from separate drug classes.
- 4.2.10 Subgroup only exclusion criteria: prior administration of ferumoxytol.

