4.3 Pre-Screen

Subjects will be initially evaluated in a variety of OHSU clinics or the inpatient setting to determine their eligibility. Possible clinics include; neuro-oncology, stroke, multiple sclerosis, cardiology, cardiothoracic, vascular surgery, hematology clinics, or inpatient services to determine possible candidacy for the study by one or more of the clinical investigators. If study participation is appropriate and the subject fulfills the eligibility criteria, they will be invited to participate.

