4.4 Subject Registration

Following appropriate pre-registration evaluation, a signed consent, HIPAA authorization, and completed eligibility checklist will be obtained. New subject registrations will be submitted to the study coordinator, who will record study data on all subjects entered into the study and complete subsequent forms.

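### Section 4.7.3 allows up to three repeat ferumoxytol administrations without requiring the safety exclusions in 4.2 to be re-confirmed

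*Combined protocol and SAP*

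**What the plan says.** Section 4.7.3 states: "If there are no adverse events, the already enrolled subjects may repeat the study visit (days 1, 2, 3 and 4". On spacing and number it adds: "This may be repeated at least 30 days apart, for up to a total of 4 study visits". A repeat visit includes the day 2 ferumoxytol administration, which 4.5 caps at 510 mg. Two tests are named for repeat visits. One is creatinine/GFR, tied to gadolinium given on study; for the other, "a pregnancy test in women of child bearing potential will be done at each subsequent visit".

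Eligibility is placed at the start. Section 4.3 says "Subjects will be initially evaluated in a variety of OHSU clinics or the inpatient setting to determine their eligibility", and 4.4 requires that before registration "a signed consent, HIPAA authorization, and completed eligibility checklist will be obtained". No other section asks for either step again.

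The exclusions in 4.2 include "Subjects with known hepatic insufficiency or cirrhosis" (4.2.4), "Subjects with known or suspected iron overload (genetic hemochromatosis or history of multiple transfusions" (4.2.5) and, in 4.2.7, "HIV-positive patients on combination antiretroviral therapy are ineligible because of the potential for pharmacokinetic interactions with ferumoxytol". Section 4.2.3 excludes hypersensitivity to parenteral iron or dextran products, 4.2.8 pregnancy and lactation, and 4.2.9 three or more drug allergies across separate classes.

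**The concern.** Most of the exclusions describe a state that can change. Between two visits a subject may be transfused, be diagnosed with liver disease, start antiretroviral therapy, react to an iron product given elsewhere, acquire a further drug allergy or begin breastfeeding. Followed as written, 4.7.3 would let that subject receive another administration from which a new subject in the same state is barred.

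A tolerated earlier dose does not replace the check. The boxed warning reproduced in 2.6.2.2 says that hypersensitivity has occurred after a tolerated dose.

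There is a smaller reporting consequence. The descriptive safety summary (objective 3.2.2, section 6.1) would pool such exposures with the rest. Because the change in status need not be recorded, a reader could not separate them.

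**Working it through.** No figure in the plan needs reproducing. The check sets each general exclusion beside whatever the protocol requires at a repeat visit.

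| Exclusion | Stated check before a repeat dose |
|---|---|
| 4.2.1 herniation signs | none |
| 4.2.2 MRI contraindication | none |
| 4.2.3 parenteral iron/dextran hypersensitivity | none for reactions off study; a reaction to study drug is an adverse event and bars repetition |
| 4.2.4 liver insufficiency, cirrhosis | none; 4.7.5 records laboratory values without naming them |
| 4.2.5 iron overload, transfusions | none |
| 4.2.6 hemodynamic instability | blood pressure and heart rate before the first infusion at each visit (4.7.5) |
| 4.2.7 antiretroviral therapy | none |
| 4.2.8 pregnancy, lactation | pregnancy test; nothing for lactation |
| 4.2.9 drug allergies | none |

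Seven of the nine (4.2.1 to 4.2.5, 4.2.7, 4.2.9) have no stated re-check, and 4.2.8 is half covered. The GFR test does not fill the gap: it controls gadolinium, and renal disease is a reason to study ferumoxytol (3.1.4), not to withhold it.

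Next, could another provision catch a change?

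- **Adverse-event condition.** Section 4.7.5 confines recording to events related or potentially related to ferumoxytol. A transfusion for another illness or a new antibiotic allergy falls outside it.
- **Follow-up contact (4.7.4).** It is for adverse events, at roughly 4 to 6 weeks, that is 28 to 42 days. Repetition is allowed from day 30, so the contact can come up to 42 - 30 = 12 days after the next dose becomes permissible.
- **Withdrawal criteria (8.3.4).** These include clinically significant laboratory abnormality, protocol violation and the investigator's judgment. They schedule no enquiry and do not list newly meeting an exclusion.

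Dose and occasions:

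- Repeat administrations per subject: 4 - 1 = 3.
- Iron from repeats: at most 3 x 510 = 1,530 mg. Iron in total: at most 4 x 510 = 2,040 mg.
- Section 2.6.2.1 argues that screening for iron overload is unnecessary because about 0.5 g is harmless. That covers one visit.
- Enrolment ceiling (4.6): 260 + 25 + 10 = 295. Repeat administrations: 0 to 295 x 3 = 885.
- For scale, the toxicity data in 2.6.2.2 give 671 infusions in 331 subjects, so 671 - 331 = 340 (50.7%) were second or later. Assuming the same ratio, 295 x 340/331 = about 303. Those data pool several protocols, so this is not a forecast.

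The last two figures count occasions for a re-check. They do not count doses in subjects who have become ineligible, a number the documents give no means of estimating.

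**The case against.** The strongest reply is that the exclusions can be read as continuing. Sections 4.2.7 and 4.2.8 speak of ineligibility and exclusion from the study in general terms, and 8.3.4 makes a significant protocol violation a ground for stopping. A reader might infer from 4.7.3 that knowingly dosing an ineligible subject is allowed. The documents do not support that; what is missing is a step that makes someone ask. Staff may already do so, since neither the checklist nor the separate monitoring plan (7.4) is available to read. This stands as a limit on the weight of the point, but it does not show that a re-check is required.

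The safety evidence also reaches less far than it might seem. The boxed warning does not say that patients who reacted after a tolerated dose had developed an exclusion. The single anaphylactoid reaction among about 1,740 exposed patients (1/1,740 = 0.06%) was in a patient with multiple drug allergies. That supports having 4.2.9, but does not show harm from crossing its threshold between visits. A cumulative 2,040 mg is not new either: 2.6.2.1 reports two courses of 2 x 510 mg in three Phase 3 studies. Those were patients with chronic kidney disease, so this does not clear a subject who comes under suspicion of iron overload. The absence of severe, grade 4 or 5 toxicity attributed to ferumoxytol in 671 infusions is reassuring in general, but the documents do not say whether any of those subjects had a condition listed in 4.2.

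Karnofsky status (4.1.3) is likewise not re-checked. It is tempting to add it, but no section links it to ferumoxytol risk, so it is no part of this point.

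**Conclusion.** The gap is real and modest. Up to three repeat administrations per subject, each up to 510 mg, rest on conditions that leave most of the safety exclusions unasked. The conclusion depends only on the text of 4.2 to 4.4, 4.7.3 to 4.7.5 and 8.3.4, and assumes that no unseen working document supplies the step.

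The frequency of newly arising exclusions is unknown. Neither 885 nor 303 should be read as the number of affected doses. No harm has been demonstrated, and no inferential result changes, because the analysis of safety is descriptive. The change is worth making because it is specific, inexpensive and concerns a drug with a boxed warning.

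**What to change.** Add to 4.7.3: *Before each repeat ferumoxytol administration, exclusions 4.2.1 to 4.2.9 are re-confirmed by interview and chart review, covering the time since the last dose, and the result is recorded. A subject who now meets one receives no further ferumoxytol but completes the 4-6 week follow-up for doses already given.*

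The full eligibility checklist should not be repeated. Re-applying 4.1.1 could bar a Group 3 subject whose nodes had shrunk from the follow-up scan. Exclusion 4.2.10 (earlier ferumoxytol) applies only to the abdominal imaging subgroup, and 4.7.1.5 already removes re-dosed subjects from it.

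No new laboratory test is needed: 4.2.4 and 4.2.5 rest on known or suspected conditions, and the pregnancy test and vital signs are already scheduled. The cost is a few minutes of coordinator time at each repeat visit (885 visits at the very most) and possibly a few subjects who are not re-dosed, with the loss of their later images.

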4.7.4 Follow up

To assess for adverse events, the subject will be seen in an OHSU outpatient clinic or a telephone interview will be conducted approximately 4-6 weeks after the study visit..

4.7.5 Data Collection

All subjects will be registered and sign a consent form which includes HIPAA authorization prior to receiving ferumoxytol.

Data, such as patient demographic information, survival times may be also collected.

In addition to the imaging data the following data collection will occur when the ferumoxytol is administered:

- Blood pressure and heart rate will be recorded on day 2 of each study visit
 - Before the first ferumoxytol infusion
 - within 10 minutes after each ferumoxytol injection
 - 30 (\pm 5) minutes after the final ferumoxytol infusion.
- Monitoring for side effects including allergic reactions will be done during the day 2 ferumoxytol MRI session.
 - After the final ferumoxytol infusion, the subject will be monitored for adverse events for 30(\pm 5) minutes and discharged if stable.
- Height, weight and lab values of the subjects will also be recorded.

Adverse events related to or potentially related to the administration of ferumoxytol will be recorded; adverse events related to the MRI's experience itself, such as claustrophobia/anxiety, nausea with GBCA injection, or discomfort due to positioning, is not being studied and will not be reported. The adverse events that will be monitored for during the infusion include localized discomfort at the IV injection site, pain, respiratory difficulties, flushing, dizziness, pruritis/rash, and any other symptoms that could be secondary to an anaphylactoid type reaction.

All data points will be flexible as subject safety while in the magnet is first priority. In addition to monitoring the above-mentioned safety parameters, an emergency code cart is located in the MR suite and can be utilized by the MR team, as well as accessed by the code team at the institution should an emergent situation arise.

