Based on communication with AMAG Pharmaceuticals, manufacturer of ferumoxytol, all recommendations apply to iron replacement therapy where infusion rate and dilution do not impact efficacy. However, for an imaging indication certain infusion parameters are required to gain information, such as dynamic imaging. Increased infusion rate will only affect the first injection of 1 mg/kg, which is a small fraction of the full therapeutic dose, and therefore may minimally increase the risk of adverse reactions. The next two injections are given at a slower rate. The recommended 15 minutes has no scientific basis, it has been chosen arbitrarily. For MR imaging stopping the scanner for 15 minutes would be disadvantageous. Applying multiple injections, which is not the case with iron replacement therapy, may increase safety, compared to continuous injection. This may contribute to the fact that in our patient population only minor adverse reactions have been reported.

OHSU Toxicity Data

As of December 31st, 2015, a total of 671 infusions of ferumoxytol had been completed on 331 study subjects as part of OHSU's Blood Brain Barrier sponsored IRB approved protocols. The dose has ranged from 75 to 510 mg of ferumoxytol (0.5 to 11 mg/kg). In all these cases, ferumoxytol was given during MRI, using multiple IV bolus injections (1:1 diluted ferumoxytol, 3ml/s flow rate, with 20ml saline flush at the same flow rate.) In most studies the first 1mg/kg (or 75mg) was used for dynamic perfusion imaging; the remaining dose was injected in one or two subsequent bolus injections. The full 510mg was never given as a single injection. Within 42 days after ferumoxytol administration, there were 85 adverse events possibly, probably or definitely related to ferumoxytol. Among the 85 events, 43 patients had 1 event, 12 had 2 events, 3 had three events, one had 4 events and one had five events. 80% of the toxicity events occurred within 48 hours post ferumoxytol administration. There were no severe, grade 4 or 5 toxicities (CTCAE version 3 and 4) that were attributed to ferumoxytol. Table 2 shows the toxicities up to and beyond 48 hours. (Data has been published in AJNR in July of 2017).

Toxicity Category Attribute	Overall (<42 days)		Within 48 hours		>48 hours	
	# of events	Freq of events	# of events	Freq of events	# of events	Freq of events
Gastrointestinal	31	4.62%	23	3.43%	8	1.19%
Cardiac General	17	2.53%	17	2.53%	0	0.00%
Pain	17	2.53%	17	2.53%	0	0.00%

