Dermatology/Skin	7	1.04%	5	0.75%	2	0.30%
Metabolic/Lab	5	0.75%	0	0.00%	5	0.75%
Occular/Visual	2	0.30%	1	0.15%	1	0.15%
Allergy/Immunology	1	0.15%	1	0.15%	0	0.00%
Constitutional	1	0.15%	1	0.15%	0	0.00%
Hemorrhage/Bleeding	1	0.15%	0	0.00%	1	0.15%
Other	1	0.15%	1	0.15%	0	0.00%
Pulmonary/Upper Resp	1	0.15%	1	0.15%	0	0.00%
Vascular	1	0.15%	1	0.15%	0	0.00%
Total	85	12.67%	68	10.13%	17	2.53%

Table 2. Toxicities possibly, probably or definitely related to ferumoxytol administration for MR imaging. Data includes 671 administrations at OHSU between 2004 and Dec 31st 2015.

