4.7.1.3 Day 3 (late ferumoxytol MRI)

Group1: Approximately 24 hours after the ferumoxytol infusion, the subject will have a post-ferumoxytol MRI brain and/or spine, Gadolinium MRI may be repeated at the investigator's discretion based on subject's suspected or known diagnosis. Subjects with renal insufficiency (GFR <50ml/min/1.73m²) and/or contraindication to GBCA, will not receive Gadolinium. Group2 and 3 subjects will undergo MRI of the carotids, aorta or other arteries or veins or cervical lymph nodes respectively approximately 48h after ferumoxytol injection. Short abdominal MR imaging will be performed in the subgroup (24-48 hours after ferumoxytol administration).

4.7.1.4 Day 4 (2nd late ferumoxytol MRI) (at physician's discretion for groups 2 and 3)

Subjects in groups 2 and 3 who undergo vessel imaging or cervical lymph node imaging will repeat the post ferumoxytol MRI approximately 1 week (6-8 days) after the ferumoxytol infusion, at the physician's discretion. Any subject in the abdominal imaging subgroup from groups 1, 2 & 3 will undergo short abdominal MR imaging 1 week after ferumoxytol administration.

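### No adverse-event enquiry is scheduled between discharge on Day 2 and the contact at about 4-6 weeks, although subjects return for MRI at about 24 or 48 hours

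*Combined protocol and SAP*

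**What the plan says.** Objective 3.2.2 is to assess the safety of ferumoxytol given during MRI, and section 6.1 promises descriptive summaries of side effects and adverse events. Two enquiries are scheduled.

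- **Infusion session (4.7.5).** "Monitoring for side effects including allergic reactions will be done during the day 2 ferumoxytol MRI session". Also: "After the final ferumoxytol infusion, the subject will be monitored for adverse events for 30" (±5) minutes, with discharge if stable.
- **Follow-up (4.7.4).** An outpatient visit, or "a telephone interview will be conducted approximately 4-6 weeks after the study visit". Section 4.8 gives the same period and refers back to 4.7.4.

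Subjects attend again in between. For Group 1, section 4.7.1.3 says "Approximately 24 hours after the ferumoxytol infusion, the subject will have a post-ferumoxytol MRI brain and/or spine". For Groups 2 and 3 it provides for imaging of vessels or "cervical lymph nodes respectively approximately 48h after ferumoxytol injection". Section 4.7.1.4 adds a scan at about one week, at the physician's discretion in Groups 2 and 3 and for the abdominal imaging subgroup. These sections and the matching sequence tables in 5.1 list imaging only.

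Section 4.7.5 also says that events related or possibly related to ferumoxytol are to be recorded, without a time limit, and section 9.1 repeats this. On the institution's earlier experience, section 2.6.2 reports that "there were 85 adverse events possibly, probably or definitely related to ferumoxytol" within 42 days, and that "80% of the toxicity events occurred within 48 hours post ferumoxytol administration". The note to Table 2 adds: "Data includes 671 administrations at OHSU between 2004 and Dec 31st 2015".

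**The concern.** The plan's own data place most related events in the first two days. Staff see every subject inside that period or at its end, but are not told to ask anything. An event that begins after discharge and is not volunteered is first asked about some 28-42 days later.

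Mild, short-lived symptoms such as nausea, headache or dizziness are the ones a subject is most likely to forget over that interval, or to date and grade wrongly. Attribution suffers too. Section 4.7.5 excludes nausea with gadolinium injection from reporting. Gadolinium may be given in the 7 days before ferumoxytol and, in Group 1, again on Day 3. Gastrointestinal events are the largest category in Table 2 (31 of 85). A subject who recalls, a month later, feeling sick around the time of the scans is hard to assign to one agent or the other.

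**Working it through.** **1. The plan's figure.** Adding the rows of Table 2:

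- Overall: 31 + 17 + 17 + 7 + 5 + 2 + 6 × 1 = 85.
- Within 48 h: 23 + 17 + 17 + 5 + 0 + 1 + 1 + 1 + 0 + 1 + 1 + 1 = 68.
- After 48 h: 8 + 2 + 5 + 1 + 1 = 17.

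So 68/85 = 80.0%, as stated. Per administration: 85/671 = 12.67%, 68/671 = 10.13% and 17/671 = 2.53%, which also agree.

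**2. Attendance against enquiry.**

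| Time from ferumoxytol | Subject attends | Enquiry scheduled |
|---|---|---|
| Session, to 30 (±5) min after last injection | yes | yes |
| about 24 h (Group 1) | yes | no |
| about 48 h (Groups 2 and 3) | yes | no |
| about 1 week (where done) | yes | no |
| about 4-6 weeks | visit or telephone | yes |

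**3. Clock time observed.** In the Group 1 brain schedule, the scans that span the three injections take 2 + 4 + 2 + 4 + 2 = 14 minutes. Adding 25-35 minutes gives 39-49 minutes, or 1.4-1.7% of the 2,880 minutes in 48 h. If breaks stretch this to 1-3 hours (an assumption), 94-98% of the 48 h is still unobserved. This is a share of time, not of events.

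**4. Share of events first asked about at 4-6 weeks.** Let s be the fraction of the 68 early events that arise in session. With no spontaneous reports, the share is (85 − 68s)/85 = 1 − 0.8s.

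| s | Events left to the 4-6 week contact | Share of 85 |
|---|---|---|
| 1 | 17 | 20% |
| 0.75 | 34 | 40% |
| 0.5 | 51 | 60% |
| 0.25 | 68 | 80% |
| 0 | 85 | 100% |

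The share passes one half when s is below 42.5/68 = 0.625. The documents do not give s.

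**5. What a Day 3 enquiry would change.** If Day 3 falls at 48 h (Groups 2 and 3, up to 25 + 10 = 35 subjects), the share left to a later contact falls to 17/85 = 20%, whatever s is. Group 1 is up to 260 of 295 subjects (88%) and returns at about 24 h. If f is the fraction of the 68 that arises between 24 and 48 h, its share is (17 + 68f)/85 = 20% + 80% × f. Table 2 has no split at 24 h, so f is unknown.

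**The case against.** The strongest reply is that capture is wider than the two scheduled points. The sentence on recording related events has no time limit, so a symptom mentioned at Day 3 or Day 4 can be recorded now. This stands: the gap is in scheduled enquiry, not in what may be recorded. But it is passive capture, and nothing obliges staff to ask.

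Several stronger readings are tempting, and the documents do not support them:

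- A reader might take the phrase in 4.7.5 about data collected when ferumoxytol is given as confining all event recording to the session. It introduces only the bullet list (vital signs, session monitoring, height, weight, laboratory values). The recording sentence follows that list and is not bound by it.
- All 17 cardiac and all 17 pain events in Table 2 fell within 48 h, which might suggest that such events are being missed after discharge. Nothing says when in the 48 h they arose. Some could have been seen at the in-session checks.
- A reader might infer that this study could not reproduce the 48-hour split of Table 2. The event schedule of the earlier studies is not described, so this cannot be settled.

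It is also fair to say that the stakes are modest. Safety is a secondary objective, summarised descriptively in an exploratory study, and acute reactions are covered by the 30-minute observation. Recall is not the same as loss, and the documents give no loss rate. These points limit the weight of the concern but leave no reason to forgo a question at a visit that takes place anyway.

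**Conclusion.** The concern holds as a gap in scheduled enquiry. Followed as written, the plan relies on recall at about 4-6 weeks for any event that begins after discharge and is not volunteered.

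The number of events affected cannot be fixed from the documents. On Table 2's counts it lies between 20% and 100% of related events, and no narrower range has a basis. Set beside the 80% figure, the long unobserved stretch invites the reading that most events rest on recall. That does not follow, because the in-session share is not reported.

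The range assumes that event timing here resembles the earlier studies and that nothing is reported spontaneously in between. The first assumption is uncertain: section 2.6.2 describes those injections as given at 3 ml/s, whereas section 4.5 limits the second and third injections here to 1 ml/s.

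The imaging objectives are unaffected. This is a worthwhile, inexpensive improvement to a stated safety objective.

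**What to change.** In section 4.7.5, with a cross-reference from 4.7.1.3 and 4.7.1.4, add an enquiry at the Day 3 attendance, and at Day 4 where done. Before scanning and before any repeat gadolinium, staff ask about symptoms since the infusion and record each with onset date and time and CTCAE grade. Keep the 4-6 week contact for later events.

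In section 6.1, summarise events by recorded onset (in session, up to 24 h, 24-48 h, later) rather than by the visit at which they were reported, because Day 3 is at about 24 h in Group 1 and about 48 h in Groups 2 and 3. State that Group 1 events between 24 and 48 h still depend on the later contact, or on the one-week scan for those who have it.

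The cost is a few minutes per attendance, with no new visit or procedure. Reported rates of mild events may rise, and the report should say that the added enquiry may be the reason.
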